**Notes:**

- 1) For Part A, only display the category for 1 Total Dose Administered, and do not present the summary statistics. For Parts B and D, please display all categories for number of doses administered (1-5) and summary statistics. The number of doses section is the sum of full and partial doses.

Table 14.1.4 (EX\_TAA\_F\_O)  
Summary of Investigational Product Administration  
Population: Safety Analysis Set

Part: All Study Parts	Pooled MRT5005 N=xx	Pooled Placebo N=xx
Number of Total Doses Administered - n (%)		
1	xx (xx.x)	xx (xx.x)
2	xx (xx.x)	xx (xx.x)
3	xx (xx.x)	xx (xx.x)
4	xx (xx.x)	xx (xx.x)
5	xx (xx.x)	xx (xx.x)
Number of Full Doses Administered		
Mean	xx.x	xx.x
SD	xx.xx	xx.xx
Range	(xx, xx)	(xx, xx)
Number of Partial Doses Administered		
Mean	xx.x	xx.x
SD	xx.xx	xx.xx
Range	(xx, xx)	(xx, xx)

AB\_F01  
PC\_F02  
EX\_F01

Listing Source: EX\_LAB\_F\_X, EX\_LAC\_F\_X

**Medical History**

Table 14.1.5 (MH\_TAA\_F\_X)  
Medical History by System Organ Class and Preferred Term by Dose Group  
Population: Safety Analysis Set

Part: x	MRT5005 Xmg N=xx n (%)	MRT5005 Xmg N=xx n (%)	MRT5005 Xmg N=xx n (%)	Pooled Placebo N=xx n (%)
Any Medical History	xx (xx.x)	xx (xx.x)	xx (xx.x)	xx (xx.x)
System Organ Class 1	xx (xx.x)	xx (xx.x)	xx (xx.x)	xx (xx.x)
Preferred Term 1	xx (xx.x)	xx (xx.x)	xx (xx.x)	xx (xx.x)
Preferred Term 2	xx (xx.x)	xx (xx.x)	xx (xx.x)	xx (xx.x)
System Organ Class 2	xx (xx.x)	xx (xx.x)	xx (xx.x)	xx (xx.x)
Preferred Term 1	xx (xx.x)	xx (xx.x)	xx (xx.x)	xx (xx.x)
Preferred Term 2	xx (xx.x)	xx (xx.x)	xx (xx.x)	xx (xx.x)

PC\_F02  
MH\_F01

Listing Source: MH\_LAA\_F\_X

**Notes:**

- 1) *MH\_TAA\_F\_X will be produced for each study part and for the study overall.*
- 2) *Sort System Organ Class and Preferred Term within System Organ Class by descending order of overall (MRT5005 + Placebo) frequency.*

**Protocol Deviations**

Table 14.1.6 (PD\_TAA\_F\_X)  
Protocol Deviations by Type and Dose Group  
Population: Safety Analysis Set

Part: x	MRT5005 Xmg N=xx n (%)	MRT5005 Xmg N=xx n (%)	MRT5005 Xmg N=xx n (%)	Pooled Placebo N=xx n (%)
Type				
Any Protocol Deviation	xx (xx.x)	xx (xx.x)	xx (xx.x)	xx (xx.x)
Type 1	xx (xx.x)	xx (xx.x)	xx (xx.x)	xx (xx.x)
Type 2	xx (xx.x)	xx (xx.x)	xx (xx.x)	xx (xx.x)
Type 3	xx (xx.x)	xx (xx.x)	xx (xx.x)	xx (xx.x)

PC\_F02

Listing Source: PD\_LAA\_F\_X

**Notes:**

- 1) *PD\_TAA\_F\_X will be produced for each study part.*
- 2) *Sort Type by descending order of overall (MRT5005 + Placebo) frequency.*

**Adverse Events**

Table 14.3.1.1 (AE\_TAA\_F\_X)  
Overall Summary of Treatment-Emergent Adverse Events by Dose Group  
Population: Safety Analysis Set

Part: x	MRT5005 Xmg N=xx n (%)	MRT5005 Xmg N=xx n (%)	MRT5005 Xmg N=xx n (%)	Pooled Placebo N=xx n (%)
Number of TEAEs Reported	xx	xx	xx	xx
Number of Subjects with Any TEAE Reported [1]	xx (xx.x)	xx (xx.x)	xx (xx.x)	xx (xx.x)
Number of Serious TEAEs Reported	xx	xx	xx	xx
Number of Subjects with Any Serious TEAE Reported [1]	xx (xx.x)	xx (xx.x)	xx (xx.x)	xx (xx.x)
Number of TEAEs by Relationship to IP				
Not Related	xx	xx	xx	xx
Related	xx	xx	xx	xx
Number of Subjects with TEAEs by Relationship to IP [2]				
Not Related	xx (xx.x)	xx (xx.x)	xx (xx.x)	xx (xx.x)
Related	xx (xx.x)	xx (xx.x)	xx (xx.x)	xx (xx.x)
Number of Subjects with TEAEs by Relationship to Nebulization/Treatment Administration [3]				
Not Related	xx (xx.x)	xx (xx.x)	xx (xx.x)	xx (xx.x)
Related	xx (xx.x)	xx (xx.x)	xx (xx.x)	xx (xx.x)
Number of TEAEs by Severity				
Mild	xx	xx	xx	xx
Moderate	xx	xx	xx	xx
Severe	xx	xx	xx	xx
Number of Subjects with TEAEs by Severity [4]				
Mild	xx (xx.x)	xx (xx.x)	xx (xx.x)	xx (xx.x)
Moderate	xx (xx.x)	xx (xx.x)	xx (xx.x)	xx (xx.x)
Severe	xx (xx.x)	xx (xx.x)	xx (xx.x)	xx (xx.x)
Number of Subjects with TEAEs Leading to Treatment Discontinuation [1]	xx (xx.x)	xx (xx.x)	xx (xx.x)	xx (xx.x)
Number of Subjects with TEAEs Resulting in Death [1]	xx (xx.x)	xx (xx.x)	xx (xx.x)	xx (xx.x)
Number of TEAEs Classified as a Pulmonary Exacerbation by Type				
All	xx	xx	xx	xx

Investigator-Defined	xx	xx	xx	xx
Protocol-Defined	xx	xx	xx	xx
Number of Subjects with TEAEs Classified as a Pulmonary				
Exacerbation by Type [1]				
All [5]	xx (xx.x)	xx (xx.x)	xx (xx.x)	xx (xx.x)
Investigator-Defined	xx (xx.x)	xx (xx.x)	xx (xx.x)	xx (xx.x)
Protocol-Defined	xx (xx.x)	xx (xx.x)	xx (xx.x)	xx (xx.x)

AB\_F03

[1] AE\_F05  
[2] AE\_F06a  
[3] AE\_F06b  
[4] AE\_F07  
[5] AE\_F06d  
PC\_F02

Listing Source: AE\_LAA\_F\_X

**Notes:**

- 1) The rows 'Number of TEAEs Reported' and 'Number of Serious TEAEs Reported' display the total number of TEAE counts.
- 2) If a subject experiences multiple adverse events, then take the closest relationship to study drug for the row 'Number of Subjects with TEAEs by Relationship' for each relationship to IP and relationship to nebulization
- 3) If a subject experiences multiple adverse events, then take the worst case severity for the row 'Number of Subjects with TEAEs by Severity'.
- 4) In the by type summary of subjects with TEAEs classified as pulmonary exacerbations, any subject with either investigator-defined or protocol-defined will be counted once in the All row. Subjects with both an investigator-defined and a protocol-defined TEAE classified as a pulmonary exacerbation will be recorded once in each row, investigator-defined and protocol-defined.

***Non-unique tables for AE\_TAA\_F\_X:***

Table 14.3.1.1.1 (AE\_TAI\_F\_A)

Overall Summary of Treatment-Emergent Adverse Events by Dose Group Through Day 29  
Population: Safety Analysis Set

AB\_F03  
[1] AE\_F05  
[2] AE\_F06a  
[3] AE\_F06b  
[4] AE\_F07  
[5] AE\_F06d  
PC\_F02

Listing Source: AE\_LAA\_F\_A

Table 14.3.1.1.1 (AE\_TAI\_F\_B)

Overall Summary of Treatment-Emergent Adverse Events by Dose Group Through Day 57  
Population: Safety Analysis Set

AB\_F03  
[1] AE\_F05  
[2] AE\_F06a  
[3] AE\_F06b  
[4] AE\_F07  
[5] AE\_F06d  
PC\_F02

Listing Source: AE\_LAA\_F\_B

Table 14.3.1.1.1 (AE\_TAI\_F\_D)

Overall Summary of Treatment-Emergent Adverse Events by Dose Group Through Day 32  
Population: Safety Analysis Set

AB\_F03  
[1] AE\_F05  
[2] AE\_F06a  
[3] AE\_F06b  
[4] AE\_F07  
[5] AE\_F06d  
PC\_F02

Listing Source: AE\_LAA\_F\_D

Table 14.3.1.1.2 (AE\_TAK\_F\_O)  
Overall Summary of Treatment-Emergent Adverse Events by Time Interval  
Population: Safety Analysis Set

Part: x Time Interval: xx to xx	Pooled MRT5005 N=xx n (%)	Pooled Placebo N=xx n (%)
Number of TEAEs Reported	xx	xx
Number of Subjects with Any TEAE Reported [1]	xx (xx.x)	xx (xx.x)
Number of Serious TEAEs Reported	xx	xx
Number of Subjects with Any Serious TEAE Reported [1]	xx (xx.x)	xx (xx.x)
Number of TEAEs by Relationship to IP		
Not Related	xx	xx
Related	xx	xx
Number of Subjects with TEAEs by Relationship to IP [2]		
Not Related	xx (xx.x)	xx (xx.x)
Related	xx (xx.x)	xx (xx.x)
Number of Subjects with TEAEs by Relationship to Nebulization/Treatment Administration [3]		
Not Related	xx (xx.x)	xx (xx.x)
Related	xx (xx.x)	xx (xx.x)
Number of TEAEs by Severity		
Mild	xx	xx
Moderate	xx	xx
Severe	xx	xx
Number of Subjects with TEAEs by Severity [4]		
Mild	xx (xx.x)	xx (xx.x)
Moderate	xx (xx.x)	xx (xx.x)
Severe	xx (xx.x)	xx (xx.x)
Number of Subjects with TEAEs Leading to Treatment Discontinuation [1]	xx (xx.x)	xx (xx.x)
Number of Subjects with TEAEs Resulting in Death [1]	xx (xx.x)	xx (xx.x)
Number of TEAEs Classified as a Pulmonary Exacerbation by Type		
All	xx	xx
Investigator-Defined	xx	xx

Protocol-Defined	xx	xx
Number of Subjects with TEAEs Classified as a Pulmonary Exacerbation by Type [1]		
All [5]	xx (xx.x)	xx (xx.x)
Investigator-Defined	xx (xx.x)	xx (xx.x)
Protocol-Defined	xx (xx.x)	xx (xx.x)
AB_F03		
[1] AE_F05		
[2] AE_F06a		
[3] AE_F06b		
[4] AE_F07		
[5] AE_F06d		
PC_F02		
AE_F18		

Listing Source: AE\_LAA\_F\_X

**Notes:**

- 1) The first page will be "Part: All Study Parts" with "Time Interval: Overall" and will include all AEs across all study parts. The subsequent page will be: "Part: All Study Parts" with "Time Interval: 1 month post-dose". The last page will be: "Part: All Study Parts" with "Time Interval: > 1 month post-dose".
- 2) In the column headers, report the number of subjects who were at risk for an AE at the start of the interval.
- 3) The rows 'Number of TEAEs Reported' and 'Number of Serious TEAEs Reported' display the total number of TEAE counts.
- 4) If a subject experiences multiple adverse events, then take the closest relationship to study drug for the row 'Number of Subjects with TEAEs by Relationship' for each relationship to IP and relationship to nebulization
- 5) If a subject experiences multiple adverse events, then take the worst case severity for the row 'Number of Subjects with TEAEs by Severity'.
- 6) In the by type summary of subjects with TEAEs classified as pulmonary exacerbations, any subject with either investigator-defined or protocol-defined will be counted once in the All row. Subjects with both an investigator-defined and a protocol-defined TEAE classified as a pulmonary exacerbation will be recorded once in each row, investigator-defined and protocol-defined.

Table 14.3.1.2 (AE\_TAB\_F\_X)  
Summary of Treatment-Emergent Adverse Events by System Organ Class and Preferred Term by Time Interval and Dose Group  
Population: Safety Analysis Set

Part: x Time Interval: xx to xx		MRT5005 Xmg N=xx n (%) m	MRT5005 Xmg N=xx n (%) m	MRT5005 Xmg N=xx n (%) m	Pooled Placebo N=xx n (%) m
System Organ Class					
Preferred Term					
System Organ Class 1	xx (xx.x) xx	xx (xx.x) xx	xx (xx.x) xx	xx (xx.x) xx	xx (xx.x) xx
Preferred Term 1	xx (xx.x) xx	xx (xx.x) xx	xx (xx.x) xx	xx (xx.x) xx	xx (xx.x) xx
Preferred Term 2	xx (xx.x) xx	xx (xx.x) xx	xx (xx.x) xx	xx (xx.x) xx	xx (xx.x) xx
System Organ Class 2	xx (xx.x) xx	xx (xx.x) xx	xx (xx.x) xx	xx (xx.x) xx	xx (xx.x) xx
Preferred Term 1	xx (xx.x) xx	xx (xx.x) xx	xx (xx.x) xx	xx (xx.x) xx	xx (xx.x) xx
Preferred Term 2	xx (xx.x) xx	xx (xx.x) xx	xx (xx.x) xx	xx (xx.x) xx	xx (xx.x) xx

AB\_F04  
AE\_F08  
AE\_F14  
AE\_F15  
AE\_F16

Listing Source: AE\_LAA\_F\_X

**Notes:**

- 1) Repeat for each time interval. Time intervals for Part A are Overall, Study Day 1, 1 < Study Day ≤ 7, 1 ≤ Study Day ≤ 29, Study Day > 29. Time intervals for Part B are Overall, Study Day 1, 1 < Study Day ≤ 7, 1 ≤ Study Day ≤ 36, 1 ≤ Study Day ≤ 57, and Study Day > 57. Time intervals for Part D are Overall, Study Day 1, 1 < Study Day ≤ 5, 1 ≤ Study Day ≤ 11, 1 ≤ Study Day ≤ 32, and Study Day > 32.
- 2) In the column headers, report the number of subjects who were at risk for an AE at the start of the interval.
- 3) Sort System Organ Class and Preferred Term within System Organ Class by descending order of overall (MRT5005 + Placebo) frequency in subject counts.
- 4) The number of events will be summarized such that subjects with multiple TEAEs in system organ class in a time interval are counted more than once. Subjects with multiple TEAEs in preferred term in a time interval are counted more than once.

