## **2.5 Sample Size Determination**

The sample size is not based on any statistical considerations. Instead, the sample size is based on traditional phase 1 first-in-human study designs for this disease population. In Parts A and B of the study, the inclusion of 4 subjects per dose group (3 subjects randomized to MRT5005 and 1 subject randomized to placebo) will provide basic information on safety and tolerability during dose escalation of MRT5005. In Part D, 8 subjects treated at 4 mg MRT5005 or placebo (6 subjects randomized to MRT5005 and 2 subjects randomized to placebo) will provide further safety and tolerability data on MRT5005. This study is also designed with the flexibility to enroll additional groups of subjects to support meeting its objectives.

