### 9.3 Adverse Events

Adverse events will be coded using the Medical Dictionary for Regulatory Activities (MedDRA) Version 23.1 to identify the system organ class and preferred term.

Treatment-emergent AEs are defined as events that are newly reported or reported to worsen in severity after the start of treatment. Adverse events that occur after the treatment start date, occur on the treatment start date with a time that is equal to or after treatment start time, or that have a missing AE start date will be categorized as treatment-emergent. Treatment-emergent AEs will be summarized for the safety analysis set.

For summaries of TEAEs by time interval, the categorizations for Part A will be: Overall, Study Day 1, 1 < Study Day ≤ 7, 1 ≤ Study Day ≤ 29, and Study Day > 29. The categorizations for Part B will be: Overall, Study Day 1, 1 < Study Day ≤ 7, 1 ≤ Study Day ≤ 36, 1 ≤ Study Day ≤ 57, and Study Day > 57. The categorizations for Part D will be: Overall, Study Day 1, 1 < Study Day ≤ 5, 1 ≤ Study Day ≤ 11, 1 ≤ Study Day ≤ 32, and Study Day > 32. The categorizations for the study overall will be: Overall, through 1 month post-dose (Day 29, Day 57, and Day 32 for Part A, Part B, and Part D, respectively), after 1 month post-dose (> Day 29, > Day 57, and > Day 32 for Part A, Part B, and Part D, respectively). Any TEAE with a completely missing start date will not be categorized into a specific time interval, but will be included in the Overall category.

Any dose limiting toxicities identified will be addressed in the clinical study report (CSR).

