### **9.3.2 Subject-level and Event-level Summary of AEs**

A summary table will be presented for each study part by dose group to reflect a count and percentage of subjects experiencing at least 1 TEAE in each system organ class and preferred term and a count of TEAEs occurring in subjects in the safety analysis set within each system organ class and preferred term. All percentages will use the number of subjects in the safety analysis set as the denominator. Therefore, if a subject has more than 1 AE within a system organ class, the subject will be counted only once in that system organ class. If a subject has more than 1 AE that codes to the same preferred term, the subject will be counted only once for that preferred term. For the event-level summaries, subjects experiencing more than 1 AE within a system organ class or preferred term will be counted more than once for that system

organ class or preferred term. Tabular summaries will be sorted by descending overall (MRT5005 + Placebo) frequency in subject counts by system organ class and by preferred term.

Using the same subject-level and event-level counting rules, a summary table of TEAEs by preferred term will be presented for the overall time period by dose group for each study part, as well as separately through Day 29, Day 57, and Day 32 for Part A, Part B, and Part D, respectively. In addition, the summary of AEs by preferred term will be presented for the study overall for the overall time interval and through 1 month post-dose (Day 29, Day 57, and Day 32 for Part A, Part B, and Part D, respectively) by pooled treatment group.

All AEs will be presented in data listings for subjects in the safety analysis set, including a flag to distinguish if the AE was treatment-emergent.

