#### **9.4 Deaths, Serious Adverse Events, and Other Significant Adverse Events**

Treatment-emergent SAEs and adverse events of special interest will be summarized for all subjects in the safety analysis set for each study part by dose group and time interval.

Summary tables will be presented by dose group to reflect a count and percentage of subjects experiencing at least 1 TEAE in each system organ class and preferred term (subject-level analysis) and a count of TEAEs (event-level analysis) occurring in subjects in the safety analysis set within each system organ class and preferred term within each AE subset (serious, AESIs). All percentages will use the number of subjects in the safety analysis set as the denominator. Therefore, for the subject-level analysis, if a subject has one or more AE within a system organ class, the subject will be counted only once in that system organ class. If a subject has one or more AE that codes to the same preferred term, the subject will be counted only once for that preferred term. For the event-level analysis, subjects experiencing more than 1 AE within a system organ class or preferred term will be counted according to the number of AEs they experience (more than once) for that system organ class or preferred term. Tabular summaries will be sorted by descending overall (MRT5005 + Placebo) frequency in subject counts by system organ class and by preferred term.

Using the same subject-level and event-level counting rules, treatment-emergent pulmonary exacerbations (investigator and protocol-defined) will be summarized by preferred term for all subjects in the safety analysis set for each study part by dose group and time interval.

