**Notes:**

- 1) **Include Baseline (Day -1) and Days 36, 43, 57, 85, 113, 281, and 365.**

Footnotes

Data Type	Footnote Type	Code	Prefix	Footnote
All	Percent	PC_F02	Note:	Percentages were based on the number of subjects (N) in the population analyzed.
All	Baseline	BL_F01	Note:	Baseline was defined as the last measurement taken prior to the first dose, obtained on or prior to the day of first dose of study drug.
All	Baseline	BL_F01P	Note:	Baseline was defined as the Screening measurement.
All	Baseline	BL_F01S	Note:	Baseline was defined as the Day -1 complete physical exam.
All	Change from Baseline	CH_F01	Note:	Change from baseline was defined as visit value - baseline value.
All	Change from Baseline	CH_F02	Note:	Relative change from baseline was defined as (visit value - baseline value)/(baseline value)*100.
All	By Visit	VIS_F01		n = Number of subjects with the specified result at the specified visit and non-missing baseline result; nn = Number of subjects with a non-missing result at the specified visit; (%) = Percentage of subjects with the specified result at the specified visit.
All	By Visit	VIS_F01a		n = Number of subjects with the specified result at the specified visit; nn = Number of subjects with a non-missing result at the specified visit; (%) = Percentage of subjects with the specified result at the specified visit.
All	Abbreviation	AB_F01		SD = standard deviation; SE = standard error
All	Abbreviation	AB_F01a		SD = standard deviation
All	Abbreviation	AB_F02		CFTR = cystic fibrosis transmembrane conductance regulator; FEV 1 = forced expiratory volume in 1 second; SD = standard deviation
All	Abbreviation	AB_F03		AE = adverse event; IP = investigational product; TEAE = treatment-emergent adverse event
All	Abbreviation	AB_F04		AE = adverse event; TEAE = treatment-emergent adverse event
All	Abbreviation	AB_F05		CS = clinically significant; ECG = electrocardiogram; NCS = not clinically significant
All	Abbreviation	AB_F06		CFQ-R = Cystic fibrosis questionnaire-revised; SD = standard deviation; SE = standard error
DS	Percent	DS_F03	[2]	The denominator was defined as the total number of subjects who discontinued the study.
DM	Age	DM_F01	[1]	Age was calculated by (date of informed consent - date of birth)/365.25, rounded down to the next largest integer using the floor function, in years.

Data Type	Footnote Type	Code	Prefix	Footnote

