AE	Count	AE_F06b	[3]	If a subject experienced more than 1 adverse event, the subject was counted only once for the closest relationship to nebulization/treatment administration. AEs with missing relationships were classified as being Related to nebulization/treatment administration.

Data Type	Footnote Type	Code	Prefix	Footnote
AE	Count	AE_F06d	[5]	If a subject experienced more than 1 adverse event classified as a pulmonary exacerbation, the subject was only counted once in the 'All' row. Subjects with both an investigator-defined and a protocol-defined TEAE classified as a pulmonary exacerbation were counted once in each row, 'Investigator-Defined' and 'Protocol-Defined'.
AE	Count	AE_F07	[4]	If a subject experienced more than 1 adverse event, the subject was counted only once for the maximum severity. AEs with missing severities were counted as Severe.
AE	Count	AE_F07a	[2]	If a subject experienced more than 1 adverse event with a preferred term associated with the febrile reaction, the subject was counted only once for the maximum severity of any of the preferred terms contributing to the febrile reaction. AEs with missing severity were counted as Severe.
AE	Count	AE_F07b	[2]	If a subject experienced more than 1 hypersensitivity reaction, the subject was counted only once for the maximum severity of any of the hypersensitivity reactions. AEs with missing severity were counted as Severe.
AE	Order	AE_F08	Note:	Incidences were displayed in descending order of frequency of System Organ Class and by Preferred Term within System Organ Class.
AE	Order	AE_F09	Note:	Incidences were displayed in descending order of frequency of Preferred Term.
AE	Dictionary	AE_F14	Note:	System Organ Class and Preferred Term were based on the Version 23.1 of the MedDRA coding dictionary.
AE	Dictionary	AE_F14a	Note:	Preferred Term was based on the Version 23.1 of the MedDRA coding dictionary.
AE	Interval	AE_F15	Note:	Time intervals were determined by the start day of the adverse event.
AE	Count	AE_F16	Note:	n represents the number of subjects that experienced an adverse event in a given category. m represents the number of adverse events in a given category.

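### In the by-interval adverse event tables, the N in the column header (subjects at risk) and the stated percentage denominator (full safety set) are different numbers, so late-interval percentages need not equal n/N

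*SAP*

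**What the plan says.** SAP sections 9.3.1 (overall summary), 9.3.2 (system organ class and preferred term) and 9.4 (serious events and events of special interest) each contain the same rule: "All percentages will use the number of subjects in the safety analysis set as the denominator". In 9.4 the rule governs tables that are themselves produced "for each study part by dose group and time interval".

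The table specifications carry a different number. The notes to Tables 14.3.1.1.2, 14.3.1.2 and 14.3.2.3 instruct the programmer, for the column headers, to "report the number of subjects who were at risk for an AE at the start of the interval". Tables 14.3.2.1 (serious events) and 14.3.2.2 (special interest) are specified as repeats of 14.3.1.2, so they inherit the note. In all five, that N sits directly above the n (%) column.

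The footnotes do not settle the matter. Table 14.3.1.1.2 carries PC_F02: "Percentages were based on the number of subjects (N) in the population analyzed". Tables 14.3.1.2 and 14.3.2.3 have no percentage footnote; AE_F16 explains only the counts, for example "n represents the number of subjects that experienced an adverse event in a given category". Neither the SAP text nor the specifications define what being at risk means.

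**The concern.** A reader expects the percentage to be n divided by the N printed above it. Here the N comes from one rule and the percentage from another. If both are followed literally, a late-interval table could print N=2 above an entry of 1 (33.3).

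Two programmers could also reach different percentages from the same data. One would follow the SAP text; the other would take the header N as the denominator, which PC_F02 can be read to support.

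The intervals affected are the ones meant to show delayed toxicity, and safety is the primary endpoint. They cover most of follow-up: 337 − 29 = 308 days in Part A, 365 − 57 = 308 in Part B and 341 − 32 = 309 in Part D. If subjects have left before such an interval, dividing by the full safety set counts people who could no longer report an event.

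**Working it through.** **Which intervals can differ.** SAP 9.3 lists the intervals; Part B, for example, ends with "1 ≤ Study Day ≤ 57, and Study Day > 57". In the Overall interval and any interval starting on Day 1, every treated subject is at risk, so the two bases coincide. They can differ only in intervals starting later: Days 2 to 7 (Parts A and B) or 2 to 5 (Part D), and above all the intervals after Day 29, 57 and 32, with the matching page after 1 month post-dose in the pooled Table 14.3.1.1.2.

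**Group sizes.** SAP 2.5 gives "3 subjects randomized to MRT5005 and 1 subject randomized to placebo" per dose group in Parts A and B, and 6 active and 2 placebo in Part D. With four dose groups in each of Parts A and B:
- pooled placebo in Part A or in Part B: 4 × 1 = 4
- all-parts active: 4 × 3 + 4 × 3 + 6 = 30
- all-parts placebo: 4 + 4 + 2 = 10

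**Formulas.** Safety-set basis: 100 × n / N. At-risk basis: 100 × n / (N − L), where L is the number no longer in follow-up when the interval starts. The documents do not give L, so it is an assumption here.

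**Results for n = 1 and L = 1:**

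| Column | Safety set | At risk |
|---|---|---|
| Part A or B dose group | 1/3 = 33.3% | 1/2 = 50.0% |
| Part A or B pooled placebo | 1/4 = 25.0% | 1/3 = 33.3% |
| Part D 4 mg | 1/6 = 16.7% | 1/5 = 20.0% |
| Part D placebo | 1/2 = 50.0% | 1/1 = 100.0% |
| All-parts pooled active | 1/30 = 3.3% | 1/29 = 3.4% |
| All-parts pooled placebo | 1/10 = 10.0% | 1/9 = 11.1% |

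**Range over L.** With L = 0 every pair is identical. In a three-subject group with n = 1, the at-risk figure is 33.3%, 50.0% and 100.0% for L = 0, 1 and 2, while the safety-set figure stays at 33.3%. In the pooled active column, L = 3 gives 1/27 = 3.7% against 3.3%.

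The plan has no figure of its own on this point to reproduce.

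**The case against.** The strongest reply is that the plan states only one denominator. The SAP text names the safety set three times, once for tables explicitly by interval, and the shell note speaks only of column headers. PC_F02 can be read as agreeing with the text, since the population line of Table 14.3.1.1.2 is the safety analysis set. This stands in part: a reader might infer that the shells prescribe at-risk percentages, and they do not say so. It does not remove the mismatch. On this reading the header N is simply not the divisor, and nothing on the page says so. Elsewhere the specifications do state a special denominator, as in the notes to the ECG, chest x-ray and physical examination tables.

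A reader might also infer that late event rates will be understated. The documents do not support that as a finding, because they give no attrition figure. Protocol 4.5.1 asks that every discontinued subject who received product be followed to the end of the study. Protocol 4.5.2 allows replacement, and SAP 2.3 requires 4 weeks of safety follow-up for a subject to be evaluable. If a lost subject in a three-subject group were replaced, four would be treated and three at risk, so one event would be 1/4 = 25.0% against 1/3 = 33.3%. Losses are nonetheless possible: Protocol 8.1.5 requires withdrawal of a pregnant participant, and SAP 5.1 tabulates premature discontinuation.

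Finally, little information is hidden. The subject counts are printed, events and termination dates are listed by subject, and all analyses are descriptive. That holds, and it limits the weight of the point.

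**Conclusion.** The point holds as an inconsistency between the header N and the stated denominator in Tables 14.3.1.1.2, 14.3.1.2, 14.3.2.1, 14.3.2.2 and 14.3.2.3. It affects only intervals that start after Day 1, and only if someone has left follow-up by then. Under the assumption of one loss and one subject with an event, the gap is 16.7 percentage points in a three-subject dose group, 3.3 in Part D 4 mg and about 0.1 in the all-parts pooled active column; with no losses it is zero. Dilution of late incidence is therefore conditional, not established. No inference or decision rule depends on these percentages. This is a minor correction, worth making because safety is the primary endpoint and the columns are very small.

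**What to change.** In SAP 9.3.1, 9.3.2 and 9.4, state that percentages in tables by time interval use the number of subjects at risk at the start of that interval, which equals the safety set for Overall and for intervals starting on Day 1. Define at risk as still in follow-up on the first day of the interval, taken from the subject's own study part in the pooled table (Day 30, 58 or 33 for the late interval in Parts A, B and D). Replace PC_F02 on Table 14.3.1.1.2 with a footnote to that effect, and add the same footnote to the other four interval tables.

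The cost is a few sentences and one footnote, with no change to data collection or design. The downside is that late-interval percentages rest on smaller denominators and are not directly comparable with the Overall interval. Printing the safety-set N in the headers would also cure the mismatch, but it would leave late incidence diluted wherever subjects have left, and it would drop the at-risk count that the shells already require.
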